#### **17.4.5 Handling of Missing and Incomplete Data**

Missing imaging data will not be imputed; it will be assumed that the data are close to missing at random after accounting for the terms in the model for all analyses other than those described for the EMA ITT-based analyses. The EMA ITT-based analyses treat subjects for whom assessments are missing from a certain point onwards as having no treatment benefit thereafter; while the primary analysis assumes that they retained the treatment effect that they had at the point of drop-out, a sensitivity analysis treats them as having lost all treatment effect. While the primary analysis assumes that some of subjects' data might be missing at random for drop-outs, a sensitivity analysis assumes all withdrawals were treatment related. Various other sensitivity analyses, including multiple imputation, time to event, and responder analyses, will be provided to investigate the robustness of the primary and secondary analyses (see respective sections below for more detail; drop-outs are treated as non-responders or having an event of decline in these models).

Efficacy data missing for an entire outcome scale or for the majority of the scale will not be imputed unless stated otherwise. Instead, it will be assumed that the data are close to missing at random after accounting for the terms in the model. However, missing items within a subdomain or scale may be upscaled if some items of the subdomain or scale are present; the SAP will provide details of the handling of partial data for the efficacy endpoints for each scale. As automated data capturing devices are used for all efficacy assessments, the risk of missing data of this type is low. For imaging data, this type of missing data is impossible and consequently they are not subject to upscaling either.

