#### **17.4.8 Responder Analyses**

Responder analyses will be conducted for the primary and selected secondary endpoints by dichotomizing each endpoint.

For the corresponding imaging/efficacy parameter, a responder will be defined as a subject whose change from baseline is less than or equal to a threshold “T” defined as follows (these analyses will be done separately for the LMTM 16-mg/day *versus* placebo and LMTM 8-mg/day *versus* placebo groups):

- Let LSM1 be the LSM of change from baseline for the placebo group from the respective endpoint analysis
- Let LSM2 be the LSM of change from baseline for the LMTM group from the respective endpoint analysis
- Then  $T = (LSM1 + LSM2)/2$

Thresholds will be chosen based on the E-MITT, MI-MITT, or PI-MITT population-weighted LSMs from the respective model. Subjects who do not have a final assessment will be classified as non-responders.

For each separate LMTM group comparison *versus* placebo, the proportions of responders will be compared using the Cochran-Mantel-Haenszel test, adjusting for the randomization strata. Odds ratios and 95% confidence intervals will be presented.

For each of these analyses, if there is a significant effect of treatment on an imaging as well as another imaging or clinical efficacy parameter, the association between responders across these parameters at Week 52 will be assessed by using Pearson's chi-square test to analyze the resulting  $2 \times 2$  table. The number and percent of subjects in each cell of the  $2 \times 2$  table will be tabulated along with the p-value from the Pearson's chi-square test.

Responder analyses will be used to investigate associations between various endpoints. Correlation analyses will complement or replace responder-based analyses of associations in some cases.

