  CLASS treatment;
  VAR scorediff;
  EXACT KS;
  RUN;
```

For the following efficacy endpoint combinations, the correlation of their changes from Baseline to Week 52 will be analyzed (pooling the data from all three treatment groups):

- ADAS-cog11 vs. MRI whole brain volume
- ADCS-ADL23 vs. MRI whole brain volume

Sponsor:	TauRx Therapeutics Ltd.		
Protocol:	TRx-237-039		
Document Version No.:	3.0	Document Date:	07-JUN-2023

If for the respective pairwise comparison, the two Week 52 visit values are not available, the last available on-treatment visit with both respective values being available will be used. A scatter plot will compare the values for the two endpoints and will also present the p-value based on the Pearson correlation.

Sample SAS code (will be fully validated at the analysis stage):

```
PROC CORR DATA=dataset;
  VAR endpoint1 endpoint2;
  RUN;
```

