#### 5.9.4. Responder Analysis (Sensitivity)

This analysis is based on the ITTv5 population and is done separately for each of the five primary / secondary efficacy variables (ADAS-cog11, ADCS-ADL23, MRI whole brain, MRI temporoparietal lobe, and  $^{18}\text{F}$ -FDG-PET temporal lobe) and the exploratory efficacy variable Composite Scale, and furthermore separately for each HMTM group comparison versus control.

A responder will be defined as a subject whose change from Baseline to Week 52 is less or equal to a threshold  $T$  (if a larger value means greater impairment, otherwise: *more or equal*), which will be calculated based on the least squares means from the primary analysis model (in Section 5.9.2.1, including all three treatment groups together) and the respective MITTv5 population (E-MITTv5, MI-MITTv5, PI-MITTv5).

$T$  is defined as follows, with  $\text{LSM}_C$  and  $\text{LSM}_T$  the LSM change from Baseline at Week 52 in the control arm and (HMTM) treated arm, respectively:  $T = (\text{LSM}_C + \text{LSM}_T)/2$ .

Subjects who do not have a final assessment at Week 52 will be classified as non-responders. Subjects with no Baseline assessment will not be included in the analysis and counted as missing.

According to the study protocol, the proportion of responders will be analyzed using the Cochran-Mantel-Haenszel (CMH) test, adjusting for the randomization strata variables separately (severity, prior use of standard AD treatment, and region). In addition, the CMH test will be performed adjusting for the prior use of standard AD treatment stopped before Screening. Odds ratios and 95% confidence intervals will be presented.

Sample SAS code (will be fully validated at the analysis stage):

```

PROC LOGISTIC DATA=dataset;
  CLASS treatment(REF='Control');
  MODEL response=treatment;
  STRATA (rand)stratum;
  EXACT treatment;
  RUN;

```

As a sensitivity analysis a logistic regression will be applied to include the randomization strata variables simultaneously (without prior use of standard AD treatment stopped before Screening):

Sponsor:	TauRx Therapeutics Ltd.		
Protocol:	TRx-237-039		
Document Version No.:	3.0	Document Date:	07-JUN-2023

```
PROC LOGISTIC DATA=dataset;  
  CLASS treatment(REF='Control') severity(REF='moderate') region(REF='Europe')  
  prioruse(REF='None');
```

```
  MODEL response=treatment severity region prioruse;  
  RUN;
```

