For statistically significant treatment effects (p-value < 0.05) on the aforementioned five efficacy variables, the association between responders across these variables at Week 52 will be assessed by using Pearson's chi-square test to analyze the resulting  $2 \times 2$  table. The number and percent of subjects in each cell of the  $2 \times 2$  table will be tabulated along with the p-value from the Pearson's chi-square test.

Sample SAS code (will be fully validated at the analysis stage):

```
PROC FREQ DATA=dataset;  
  TABLES response1*response2 / CHISQ;  
  RUN;
```

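### The responder association test in SAP 5.9.4 is badly inflated because subjects missing Week 52 on both endpoints are coded as non-responders on both

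*SAP*

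**What the plan says.** On the responder analysis, SAP 5.9.4 says: "This analysis is based on the ITTv5 population and is done separately for each of the five primary / secondary efficacy variables". It is also done separately for each HMTM group against control. The threshold is the midpoint of the two arms' least squares means for change at Week 52.

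On missing data the SAP says: "Subjects who do not have a final assessment at Week 52 will be classified as non-responders". Only subjects without a baseline are left out. Protocol 17.4.8 has the same rule: "Subjects who do not have a final assessment will be classified as non-responders". Protocol 17.4.5 says of the sensitivity models that "drop-outs are treated as non-responders or having an event of decline in these models".

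The association test uses those same flags. Its trigger reads "For statistically significant treatment effects (p-value < 0.05) on the aforementioned five efficacy variables", and then "the association between responders across these variables at Week 52 will be assessed by using Pearson's chi-square test". The sample code is "TABLES response1*response2 / CHISQ". It has no restriction to subjects assessed on both endpoints and no stratification by arm.

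SAP 5.9.2.1 separately plans correlations of continuous changes (ADAS-cog11 and ADCS-ADL23, each against MRI whole brain volume), pooled over all three arms. Where the Week 52 pair is missing, "the last available on-treatment visit with both respective values being available will be used".

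**The concern.** Counting a missing outcome as a failure is a familiar, conservative choice when two arms are compared on one endpoint. It does not carry over to a cross-tabulation of two endpoints within subjects. A subject who leaves before Week 52 will usually lack the scales and the MRI together, so one event sets both flags to non-response. The chi-square test then detects that the same people left, whether or not response on one endpoint goes with response on the other.

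Protocol 17.4.8 says the responder analyses are meant to investigate associations between endpoints, imaging against clinical included. The test runs only after significant treatment effects, which is when a claim that imaging response tracks clinical response would be made. A significant result from the table as specified would be weak support for it.

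**Working it through.** **Inputs**
- N = 400: 200 per arm for 16 mg/day and control (SAP 5.3). For 8 mg/day versus control, N = 50 + 200 = 250.
- Missing share d = 20% to 25%: the planned withdrawal rate (SAP 5.3), first taken as missing on both endpoints.
- Responder rate p among assessed subjects: not stated in either document. A midpoint threshold gives about 50% if changes are roughly symmetric, so p = 0.5 is an assumption; 0.4 and 0.6 are also shown.
- Arms pooled in one table: an assumption, since the SAP does not say.
- Two-sided alpha 0.05: the SAP 4.1 rule for primary and secondary endpoints. None is stated for this test.

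**The plan's own figures.** The documents give no operating characteristic for this test, but their power figures confirm the planning base. With 150 per arm (200 less 25%), the standard error in SD units is √(2/150) = 0.1155.
- ADCS-ADL23: (3.4/8.5)/0.1155 = 3.46; normal power Φ(3.46 − 1.96) = 93.4%; noncentral t 93.2%.
- ADAS-cog11: (2.6/5.9)/0.1155 = 3.82; normal power 96.8%; noncentral t 96.7%.

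The t results match the stated 93.2% and 96.7%, so the plan's power rests on 25% missing at Week 52.

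**Association created by the coding rule.** Let the two endpoints be independent among assessed subjects.
- Both respond: (1−d)p²
- One responds, in each of two cells: (1−d)p(1−p)
- Neither responds: (1−d)(1−p)² + d
- Each margin is (1−d)p, which gives phi = dp / [1 − (1−d)p]
- The chi-square noncentrality is λ = N·phi², and the rejection rate is close to Φ(√λ − 1.96)

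At N = 400 and p = 0.5:
- d = 20%: cells 80, 80, 80, 160; phi = 0.10/0.60 = 0.167; odds ratio 160/80 = 2.0; λ = 11.1; rejection Φ(3.33 − 1.96) = 92%.
- d = 25%: cells 75, 75, 75, 175; phi = 0.125/0.625 = 0.20; odds ratio 175/75 = 2.33; λ = 16; rejection Φ(4 − 1.96) = 98%.

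Simulation with 40,000 tables per setting gave 91.8% and 97.9%.

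**Range** (p = 0.5 and N = 400 unless stated)

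| Setting | Rejection rate when endpoints are unrelated |
|---|---|
| p = 0.4, d = 20-25% | 65-82% |
| p = 0.6, d = 20-25% | over 99% |
| d = 15% | 74% |
| d = 10% | 44% |
| d = 20-25%, only 80% of it shared by both endpoints | 72-85% |
| 8 mg/day versus control, N = 250 | 75-89% |
| One arm only, N = 200 | 65-81% |
| N = 100 (assumed PET subset), missingness still fully shared | 39-52% |

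Adding the planned effects (0.44 SD on ADAS-cog11, 0.40 SD on ADCS-ADL23) with arms pooled raises the headline figures to 97% and 99%.

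**After restriction.** With only subjects observed on both endpoints, the simulated rate is 4.9% at N = 300 and 5.0% at N = 320. If the planned effects are present and arms stay pooled, it is about 8%. That remainder comes from treatment moving both endpoints, which is why stratification by arm is also needed.

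**The case against.** The other side has good points, and most of them narrow the finding.

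- A reader might infer that the test cannot come out negative. The range above shows otherwise: rejection falls to 44% at 10% missing and is lower again for small tables.
- A reader might infer that every planned drop-out lands in the double non-response cell. The rule concerns a missing Week 52 assessment, not stopping drug. Protocol 11.4.1 and 17.2 keep subjects on study off treatment, with their data. SAP Table 5 accepts days 320-456 as Week 52 for the scales and MRI, so late early-termination values count.
- PET pairs behave differently. Any PET value after day 1 counts as Week 52, and Protocol 15.3.3.1 requires an early-termination scan when the last was 30 or more days before. A leaver can therefore have a PET value and no Week 52 scale. Subjects without a baseline PET are excluded, not counted as non-responders.
- A reader might take this table as the plan's evidence linking imaging to clinical response. It is one item among several: SAP 5.9.2.1 and 6.12 plan continuous correlations, and Protocol 17.4.8 allows correlations to complement or replace the responder associations.
- The 50% responder rate and the pooling of arms are assumptions.
- The section is a sensitivity analysis, and no primary decision depends on it.

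None of this removes the mechanism. Nothing in either document restricts the table or corrects for shared missingness, and at 15% missing the false-positive rate is still about 74%.

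**Conclusion.** The concern holds in this form: as specified, the test is badly inflated for the ADAS-cog11, ADCS-ADL23 and MRI pairs in 16 mg/day versus control. Under the planning inputs and the three assumptions named (about half of assessed subjects responding, arms pooled, 20-25% missing on both endpoints), it rejects in about 92-98% of trials with unrelated endpoints. Milder assumptions lower the figure, and PET pairs are less affected. A significant result would therefore say little about whether response on one endpoint goes with response on the other. The documents do not support going further: the test can be negative, it is not the only association evidence, and neither the primary comparison nor the responder comparison between arms is compromised.

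**What to change.** In SAP 5.9.4, run the association test on subjects with an observed Week 52 value on both endpoints, stratified by randomized arm (Cochran-Mantel-Haenszel over arms). Keep missing Week 52 as non-response in the comparison of arms only.

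SAP section 10 records that v3.0 followed the data snapshot and partial unblinding for the double-blind analysis, and the non-responder rule is also protocol text. The restricted test should therefore be reported beside the planned table and labelled as added, not substituted for it.

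As a minor companion step, repeat the SAP 5.9.2.1 correlations on observed Week 52 pairs with adjustment for arm. The planned version can mix shorter with full follow-up and pools all arms; the size of that effect was not calculated.

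The cost is about 20-25% fewer subjects in this one table (300-320 instead of 400), and its result describes assessed subjects only. No new data are needed.

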#### 5.9.5. Time-to-event/Decline Analysis (Sensitivity)

This analysis, based on the ITTv5 population, will include off-treatment measurements (TOTOS) and will be done separately for the primary and secondary efficacy variables ADAS-cog11, ADCS-ADL23, and MRI whole brain volume. It will only compare subjects on HMTM 16 mg/day and control.

Time-to-event/decline will be calculated as date of onset of decline – date of first dose + 1 and will use only data from the double-blind treatment phase and upscaled values for the two co-primary endpoints.

Time of onset of decline is the first of two consecutive measurements with worsening, whereas worsening is defined as an impairment, with respect to the Baseline value of at least a change in units as outlined here:

- ADAS-cog11, ADCS-ADL23: 1
- MRI whole brain volume: 6,500 (mm^3 =  $\mu$ L)

If the threshold of the MRI whole brain volume does not appear to be reasonable once the unblinded randomization codes are used, these can be modified slightly (similarly if a model may not converge).

If the available Week 52 value (or the value of the last assessment in general, in case of early termination) is worsened without a prior worsening, an onset of decline will be triggered at Week 52 (or the respective last visit) for that subject. Subjects without any decline will be censored at the date

Sponsor:	TauRx Therapeutics Ltd.		
Protocol:	TRx-237-039		
Document Version No.:	3.0	Document Date:	07-JUN-2023

of last assessment, but if a subject missed the scheduled visit, the subject is censored at the target day of the scheduled visit.

Any missing efficacy/imaging value for a scheduled visit will be treated as a worsening from baseline, for that visit, but a single missing value at the last planned visit without a missing value or without a worsening in the previous visit will not count as a decline. If the time of onset is missing due to a missed scheduled visit the scheduled date of the missing visit will be used.

The Cox proportional hazards model with effects for treatment group and the randomization stratification variables will be used to compare HMTM 16 mg/day versus control by way of Hazard Ratio, 95% confidence interval, and p-value. A graph and a table of the Kaplan-Meier estimates will be provided.

Sample SAS code (will be fully validated at the analysis stage):

```
PROC PHREG DATA=dataset PLOTS(OVERLAY)=SURVIVAL;  
  CLASS subject treatment(REF='Control') severity(REF='moderate') region(REF='Europe')  
  prioruse(REF='None');  
  MODEL time *status(0) = treatment severity region prioruse;  
  ID subject;  
  RUN;
```

One version will be based on the visit windows (nominal data), and another will use actual dates (continuous data).

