## 17 STATISTICAL ANALYSIS

A SAP will be finalized and signed off prior to database lock and unblinding. The SAP will provide details about the planned analysis. A brief overview of the plans for the primary analysis and selected secondary and exploratory analyses is given in the following sections. Specific ROI and SPM techniques and comparisons to previous Phase 3 data or external databases as well as Population PK analyses will be described in the SAP or a corresponding additional SAP where necessary; the SAP will provide details.

Changes to the planned analysis will be documented in the SAP prior to database lock and unblinding. Deviations from the SAP (if any) will be noted in the clinical study report.

The primary target of estimation is the difference in ADAS-cog11 and ADCS-ADL23 over 52 weeks in subjects receiving the LMTM dose of 16 mg/day as compared to placebo.

The primary efficacy analyses for FDA will be performed on the Efficacy Modified Intent-to-Treat (E-MITT) which will include all randomized subjects who took at least one dose of study drug and have a baseline and a valid post-baseline efficacy assessment, and for EMA on the Intent-to-Treat (ITT) population with conservative assumptions about disease progression made for subjects who have missing post-baseline assessments. Subjects will be analyzed in the treatment group and according to the stratification variables to which they were randomized.

Changes from baseline to Week 52 on the co-primary efficacy endpoints and other modalities with repeated measures such as MRI will be analyzed using a linear mixed model for repeated measures with unstructured covariance matrix (this assumption about the covariance matrix might be relaxed if the model does not converge; the SAP will provide details). The linear mixed model will contain fixed effects for time, treatment, and a treatment-by-time interaction; additionally, the baseline value of the corresponding endpoint will be included as a covariate and the randomization stratification variables of prior usage of AChEIs and/or

memantine, MMSE split (16-19, 20-25 or 26-27) as determined at Screening, and region will be included as fixed effects in the model. F-FDG-PET and other modalities with only one planned post-baseline assessment will be analyzed using an ANCOVA; the covariates for this model will be adjusted accordingly by removing terms with time.

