#### **17.4.9 Time-to-Event Analyses**

Time-to-Event/Time-to-Decline analyses will be performed for a selected subset of endpoints as repeated measurements over time are needed. The distributions of time-to-decline in the key parameters will be summarized using the Kaplan-Meier method, with onset of decline defined as the first of two consecutive measurements that are worse than the baseline score, allowing for a certain margin which will be predefined in the SAP prior to database lock and unblinding; typical margins for the two primary endpoints are 1 unit. If there is no onset of decline prior to Week 52 and if Week 52 has a marked worsening as specified in the SAP for a given subject, an onset of decline will be triggered at Week 52 for that subject.

Time-to-decline will be calculated as date of onset of decline – date of randomization + 1.

The time-to-decline analyses are based on visit window. One measurement per visit window is selected, including off-treatment measurements. Subjects without any decline will be censored at the date of last assessment, but if a subject missed the scheduled visit, the subject is censored at the target day of the scheduled visit. The analysis will be run for the ITT population.

Any missing efficacy/imaging value for a scheduled visit will be treated as a worsening from baseline, for that visit. Because of this convention for missing values, it is possible that the first of two consecutive measurements that are worse than the baseline score by the defined amount occurs at a missed visit. In that case, since there is no date associated with the missed visit, the time-to-decline will be calculated based on the scheduled date of the missing visit.

The Cox proportional hazards regression model with effects for treatment group (two or three levels depending on whether primary or sensitivity comparison) and the randomization stratification variables will be used to compare LMTM 8 mg/day *versus* placebo (and LMTM 16 mg/day *versus* placebo, respectively) by way of Hazard Ratio, 95% confidence interval, and p-value (for alpha 0.05). A graph of the Kaplan-Meier estimates will be provided.

There will also be versions of this analysis using actual dates.

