## **4. STATISTICAL METHODS**

### **4.1. General Methods**

All outputs will be incorporated into Rich Text Format (RTF) files, sorted, and labeled according to the International Council for Harmonisation of Technical Requirements for Pharmaceuticals for Human Use (ICH) recommendations, and formatted to the appropriate page size(s).

Tabulations will be produced for appropriate demographic, Screening, Baseline, efficacy, and safety parameters. For categorical variables, summary tabulations of the number and percentage within each category (with a category for missing data) of the parameter will be presented. For continuous variables, the mean, median, lower quartile (Q1), upper quartile (Q3), standard deviation, minimum and maximum values will be presented. Time-to-event data will be summarized using Kaplan-Meier Methodology using 25th, 50th (median), and 75th percentiles (if available) with associated two-sided 95% confidence intervals (Hall-Wellner Bands), as well as percent of censored observations.

Formal statistical hypothesis testing will be performed on the primary and secondary efficacy endpoints with all tests conducted at the two-sided, 0.05 level of significance.

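### SAP 5.9.5 lets the MRI whole-brain decline threshold be changed once treatment codes are in use, although the protocol requires it to be fixed before unblinding

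*SAP*

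**What the plan says.** Protocol 17.4.9 defines onset of decline as worsening sustained over two measurements, "allowing for a certain margin which will be predefined in the SAP prior to database lock and unblinding". It attaches an alpha of 0.05 to the p-value from the Cox comparison. Protocol 17 adds a general rule: "Changes to the planned analysis will be documented in the SAP prior to database lock and unblinding".

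SAP 5.9.5 carries this out for ADAS-cog11, ADCS-ADL23 and MRI whole brain volume, comparing 16 mg/day with control in the ITTv5 population. "Time of onset of decline is the first of two consecutive measurements with worsening", and a missed visit counts as worsening, with an exception for a single miss at the last visit. The margin is 1 unit for each clinical scale. For imaging it is "MRI whole brain volume: 6,500" mm³. The SAP then says that, if the MRI threshold "does not appear to be reasonable once the unblinded randomization codes are used, these can be modified slightly", and it extends the same latitude to a model that may not converge.

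The section is headed as a sensitivity analysis. SAP section 10 records that version 3.0 was written after the data snapshot and after part of the study team had been unblinded.

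**The concern.** A cut-off that defines the event can be moved to the value that best separates the arms if it is chosen when the arms are known. The protocol's timing rule exists to prevent that, and the SAP permits exactly the timing the protocol rules out. The discretion has no stated limit: the SAP does not say what would make 6,500 mm³ unreasonable, how large a slight change may be, who decides, or whether the 6,500 mm³ result must still be shown.

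Treatment codes are not needed for the purpose the SAP gives. Whether a threshold yields too many or too few events can be seen in blinded pooled data. Changing the event definition is also not a remedy for a model that fails to converge.

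What is at stake is the value of this analysis as a robustness check. Protocol 17.4.5 lists time-to-event analyses among those meant to test the primary and secondary results, and whole brain atrophy stands first in the secondary sequence of SAP 5.9.3. A check that can be tuned with the arms known offers weak support.

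**Working it through.** **Inputs from the documents**
- Threshold 6,500 mm³; two-consecutive-visit rule; last-visit rule; missing counted as worsening (SAP 5.9.5).
- Visits at Weeks 13, 26, 39 and 52.
- 200 per arm, with 20% to 25% withdrawal (SAP 5.3); the midpoint of 22.5% is used.
- Alpha 0.05 (Protocol 17.4.9). It is taken as two-sided because SAP 4.1 describes formal testing "with all tests conducted at the two-sided, 0.05 level of significance"; that sentence concerns the primary and secondary endpoints, so applying it here is a reading.

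**Inputs assumed, not in the documents**
- Mean whole-brain loss μ of 8,000 to 20,000 mm³ per year.
- Between-subject SD of 0.6μ.
- Visit noise SD σ of 2,500 to 5,000 mm³.

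**Step 1. Check the design figures.** With 25% withdrawal, n = 200 × 0.75 = 150 per arm. For ADCS-ADL23 the noncentrality is 3.4 / (8.5 × √(2/150)) = 3.46, giving power of 93.4% (normal) or 93.2% (t); SAP 5.3 states 93.2%. For ADAS-cog11 it is 2.6 / (5.9 × √(2/150)) = 3.82, giving 96.8% or 96.7%; SAP 5.3 states 96.7%. The arm size and withdrawal rate are therefore being read as the plan uses them.

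**Step 2. Reproduce the nominal level with the threshold fixed.** Trials were simulated with no difference between arms. Subject i at week t loses bᵢ × t/52 + noise, with bᵢ ~ N(μ, (0.6μ)²) and noise ~ N(0, σ²). Dropouts leave at a uniform time and all their later visits are missing. The SAP's event rules are applied at 6,500 mm³. The arms are compared by an unstratified log-rank statistic z = (O − E)/√V, which stands in for the covariate-adjusted Cox test. There were 3,000 trials per scenario. The rejection rate is 0.044 to 0.053, against a Monte Carlo standard error of √(0.05 × 0.95/3,000) ≈ 0.004. A fixed threshold therefore holds 5%.

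**Step 3. Allow the most extreme choice.** In the same trials the largest |z| is kept over 11 equally spaced thresholds from 6,500(1 − g) to 6,500(1 + g). At g = 10% that range is 5,850 to 7,150 mm³. Two-sided rejection rates:

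| μ / σ (mm³) | fixed | ±5% | ±10% | ±20% | ±50% |
|---|---|---|---|---|---|
| 8,000 / 2,500 | 0.052 | 0.083 | 0.098 | 0.119 | 0.162 |
| 13,000 / 2,500 | 0.049 | 0.076 | 0.090 | 0.113 | 0.154 |
| 13,000 / 5,000 | 0.053 | 0.082 | 0.093 | 0.111 | 0.159 |
| 20,000 / 4,000 | 0.044 | 0.073 | 0.083 | 0.100 | 0.139 |

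In the direction favouring the drug, where the nominal level is 0.025, the rates are 0.021 to 0.025 with the threshold fixed, 0.040 to 0.049 at ±10% and 0.051 to 0.061 at ±20%.

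**Step 4. Compare with how the SAP treats similar choices.** The responder threshold in SAP 5.9.4 depends on the data, but through a set formula that leaves no choice. SAP 6.10 describes a plan to revise the non-inferiority margin after results were known, and then states that the original margin stands. SAP 5.9.2.1 deals with non-convergence of the mixed model by simplifying the covariance structure and then dropping covariates. The MRI threshold has no formula, no closing statement and no model-based fallback.

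**The case against.** The strongest reply is that little hangs on this. The analysis is labelled sensitivity. The formal analysis of whole brain atrophy is the mixed model in SAP 5.9.3.1, which does not use the threshold. The co-primary tests do not use it either, and the permission names only the MRI threshold, so the 1-unit margins for ADAS-cog11 and ADCS-ADL23 stay fixed. All of this stands and limits the point to one analysis.

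The second reply is that the permission is conditional. The SAP does name a value in advance, allows a change only if that value looks unreasonable or a model may not converge, and describes the change as slight. It does not tell anyone to search for the smallest p-value. This also stands: the Step 3 figures are upper bounds, ±50% could hardly be called slight, and the two-sided rates include choices that favour control.

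A reader might go further and infer that the threshold was changed, that the p-value is already not a 5% test, or that the first secondary endpoint is compromised. The documents do not support any of these. Version 3.0, written after partial unblinding, still prints 6,500 mm³, and neither its modification history nor section 10 mentions a change to this threshold. If 6,500 mm³ was kept, the test stays at its nominal level.

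Some protection exists elsewhere: Protocol 17 has deviations from the SAP noted in the study report, and SAP 1.1 has unplanned analyses identified there. But a change that the SAP itself permits need not count as either, so these safeguards may not catch it.

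**Conclusion.** The permission is wrong as written. It directly contradicts Protocol 17.4.9, and no bound or reporting duty limits it. If it is used, the MRI time-to-decline hazard ratio, p-value and Kaplan-Meier curves cannot be presented as a pre-specified analysis at 5%. In the worst case, choice within ±10% takes two-sided type I error from about 5% to about 8–10%.

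That size rests on assumed atrophy rates, between-subject spread and scan noise, on a log-rank test in place of the Cox model, and on always taking the most extreme threshold. The direction is the same across all four scenarios; the exact figures should be read as illustration. The consequence is confined to one sensitivity analysis. It should be corrected, but it does not threaten the trial's main conclusions.

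**What to change.** - Delete the sentence in SAP 5.9.5 and keep 6,500 mm³ as the fixed threshold.
- If the Cox model does not converge, drop the stratification covariates in the order already used in SAP 5.9.2.1: region, then prior AChEI/memantine use, then MMSE severity. Leave the event definition alone.
- Deletion alone cannot restore pre-specification, because version 3.0 post-dates partial unblinding. State in SAP section 10 or in the study report whether 6,500 mm³ was the threshold used.
- Report the 6,500 mm³ result in every case. Show any other threshold only beside it, labelled post hoc.

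The cost is a few lines of text. No new data, design change or additional analysis is needed unless another threshold was used, in which case the 6,500 mm³ analysis has to be run and shown as well.
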